- The possible combination of plasma levels of TNF-, α IFN-1, BAFF (B-cell activator factor) and thalidomide levels in the blood and saliva with the therapeutic response and the adverse effects.

Secondary:

- Evaluate the possible association between TNF-levels, adjoin molecules, apoptosis markers and growth factors in skin biopsy samples with efficacy and adverse effects.

- Evaluate the presence of fine fiber neuropathy in skin biopsy specimens.

- Establishment of a pharmacokinetic-pharmacodynamic model of thalidomide dose reduction in patients with SLE.

NUMBER OF INDIVIDUALS

40 patients with lupus (SLE) and active cutaneous involvement will be included.

STUDY DESIGN

A prospective study for a period of 12 months with adult patients with SLE (according to the classification criteria of the American College of Rheumatology- ACR) (Hochberg, 1997) with active skin lesions at the entrance regardless the use of hydroxychloroquine and/or dapsone and/or prednisone and/or immunosuppressants, and who are eligible for the use of thalidomide (see inclusion criteria) (Ministry of Health, 2013; System for Thalidomide Education and Prescribing Safety, Zeldis et al., 1999).

The initial dose of thalidomide will be 100 mg/day for 3 months and reduced to 50 mg/day and 25 mg/day, at any time depending on the therapeutic response until complete 12 months of treatment.

All patients will be treated simultaneously with hydroxychloroquine, unless there is contraindication for use of this medication.

The other drugs used for SLE control will be maintained during the study, including prednisone (with subsequent gradual dose decrease in case of improvement of skin lesions).

Patients will be clinically evaluated at baseline, then 1 month, 6 months and 12 months after inclusion for:

- the global activity of the disease through the SLEDAI-2K (Systemic Lupus Erythematosus Disease Activity Index 2000) (Gladman et al., 2002);

- the index of activity and skin severity (CLASI) (Albrecht et al., 2005);

- possible adverse effects and adherence by the Medication Adherence Self-report Inventory (MASRI) applied by a pharmacist not directly involved in patient care (Koneru et al., 2007);

- quality of life by the visual analog scale and the SF36 questionnaire (Mosca et al., 2010).

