Plasma levels of TNF-, IFN-1, BAFF, transforming growth factor-beta (TGF- β) and thalidomide levels in the blood and saliva will be performed at zero time, at 30 days, 3 months, 6 months, 9 months and 12 months.

The clinical evaluation of peripheral neuropathy will be performed at each consultation by anamnesis and through THE ENMG at baseline, at 6 months and at 12 months.

Skin biopsy of an active lesion will be performed at baseline for histological evaluation, including the study of immunohistochemistry expression of TNF-, TGF $\alpha\beta$ (Kuhn et al., 2010; Yu et al., 2013) and plasmacytoid and pro-apoptotic dendritic cell markers such as caspase 3, CD25, CD35, CD21, CD36, CD68, CD31, detection of IgG, IgM, C3 and T and B cell markers (Bălănescu et al., 2010).

Skin biopsies of uninjured skin will be obtained from the thigh area, at baseline and at 6 months for the fine fiber neuropathy assessment through immunostaining with PGP 9.5 (Birnbau & Bingham, 2014).

- Pharmacokinetic-pharmacodynamic model of use of thalidomide will be performed in two groups of 5 patients with different doses (50 mg/day and 100 mg/day).

Outcomes: evaluations on days 0 and 30.

a) Improvement in skin symptoms and severity scores [(Cutaneous Lupus Area and Severity Activity Index score (CLASI)]. Change in CLASI score assessing the activity/severity criteria from 0 to 70 will be performed. The reduction represents an improvement in skin injury related to lupus in terms of activity and/or severity. CLASI evaluates erythema and scar/hypertrophy/atrophy in 13 anatomical areas. Membrane lesions and alopecia are also part of this index.

b) Cytokine dosage. Plasma levels of TNF- α and IFN-1 will be determined by Luminex MAP (EMD Millipore Corporation®). Plasma samples will be stored at -80oC until use.

TARGET POPULATION

Inclusion criteria:

- Adult patients with SLE (according to the classification criteria of the American College of Rheumatology) (Hochberg, 1997) with active skin lesions at the entrance to the research despite the use of hydroxychloroquine and/or prednisone and/or immunosuppressants who are eligible for thalidomide use.

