- Male patients (who agree to use condoms during the entire period of treatment with thalidomide and up to 30 days after the end of it, even if they have already undergone vasectomy*) and women without fertility potential [i.e., who are in the postmenopausal phase (with amenorrhea > 1 year and confirmed by estradiol, FSH and LH levels), or who have undergone tubal ligation or hysterectomy] and who agree to the use of this drug according to the Term of Responsibility/Clarification to the introduction of thalidomide and each renewal of the prescription (Ministry of Health, 2013).

- Wish to participate in the study according to the signed TCLE.

- NORMAL ENMG at study entry.

Exclusion criteria:

Alcoholism.

- The patient's desire not to participate or leave the study at any time (without any harm to their care).

- History of peripheral neuropathy.
- Previous history of thrombophilia or presence of positive antiphospholipid antibodies.
- Renal and/or central nervous system and/or hematological activity (hemolytic anemia and/or platelet to < 50,000 platelets) concomitantly.

*Condoms will be provided by researchers (Ministry of Health, 2013).

RELEVANT METHODS

Laboratory determinations

HPLC MS/MS: The determination of blood and salivary levels of thalidomide will be performed by HPLC and tandem mass spectrometry (Teo et al., 2004).

- Pharmacokinetic analysis: The pharmacokinetic parameters of thalidomide will be calculated in the 24 h dose range based on the total plasma concentration versus time curves. The Winnonlin program, version 4.0 (PharsightCorp., Mountain View, California, USA) and the Non-linear mixed effect (NONMEN) program will be employed. The area under the plasma concentration versus time curve will be calculated in the 24-h dose interval by the trapezoid method on days 0 and 30. The apparent total clearance (CIT/F) will be obtained through the equation: $CIT/F = Dose/AUC_{0-24}$. The apparent volume of distribution (Vd/F) will be calculated by the standard software equation. The free concentration of thalidomide will be determined by the dosage in saliva. The PK-PD analysis will be performed using as pharmacokinetic parameters the total and free plasma concentrations of thalidomide and, as a pharmacodynamic parameter, we will use the clinical/laboratory indices obtained by the evaluation of SLEDAI-2K (American College of Rheumatology). The PK-PD model will be developed using the non-linear mixed effect (NONMEM).

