In addition, we hope to determine whether the mechanism of thalidomide-induced neuropathy would target thin nerve fiber injury to histological skin analysis of patients treated with this medication.

SAMPLE SIZE

This is a convenience sample.

STATISTICAL PLAN

Patients with vs. without therapeutic response to thalidomide and vs. without signs of peripheral polyneuropathy will be compared for categorical variables by fisher's exact or chi-square test and, as for

quantitative variables, by t-Student or Mann-Whitney tests, when applicable. The influence of the different variables on disease activity and polyneuropathy will be evaluated by multivariate analysis.

References

- Ackerman, AB. Histologic diagnosis of inflammatory skin diseases. Philadelphia, Lea & Febiger, 1978. P. 813.
- Agency for Healthcare Research and Quality. Priority Areas for National Action: Transforming Health Care Quality. Rockville, MD: Agency for Healthcare Research and Quality; 2003.
- Bernstein HN. Ocular safety of hydroxychloroquine. *Ann Ophthalmol.* 1991;23(8):292-6.

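### Project 2 schedules thalidomide levels by calendar visit only, with no provision for time since the daily dose, so the level–response and level–neuropathy comparisons mix exposure with sampling time

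*Combined protocol and SAP*

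**What the plan says.** The primary objective of Project 2 is to relate plasma TNF-alpha, IFN-1, BAFF and "thalidomide levels in the blood and saliva with the therapeutic response and the adverse effects". The Study design section fixes the draws by calendar: "thalidomide levels in the blood and saliva will be performed at zero time, at 30 days, 3 months", with further draws scheduled at half a year, nine months and one year. The Project 2 text gives no hour after dose, no trough or peak rule, and no instruction to note when the last dose was taken or the sample drawn. The thalidomide handling text under Relevant methods covers cooling, acidification, storage and assay only.

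Dosing is daily and changes during follow-up: "The initial dose of thalidomide will be 100 mg/day for 3 months and reduced to 50 mg/day and 25 mg/day". The same section lets each reduction follow the patient's response rather than a set date.

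The Pharmacokinetic analysis paragraph does use time. The area under the concentration curve "will be calculated in the 24-h dose interval by the trapezoid method on days 0 and 30". According to Study design, this pharmacokinetic-pharmacodynamic work covers two groups of five patients, at 50 and 100 mg/day.

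On size, "40 patients with lupus (SLE) and active cutaneous involvement will be included"; the Sample size section adds "This is a convenience sample". The Statistical plan compares patients with and without response, and with and without polyneuropathy, by t or Mann-Whitney tests for quantitative variables. It adds a multivariate analysis whose variables are not listed.

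**The concern.** A level taken a few hours after a dose and one taken half a day later can differ a good deal in the same patient on the same dose, unless the drug is eliminated very slowly. For hydroxychloroquine the documents rely on slow elimination: Subproject 1A cites the long half-life in support of blood levels, and Subproject 1C puts it at about 40 days. Over 24 hours such a drug falls by a factor of 2^(1/40) = 1.02, so draw time hardly matters. No such argument is made for thalidomide, and the plan's own AUC over the dose interval assumes that its level moves.

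Random variation in draw time pulls any relation between level and response, or level and neuropathy, towards zero. If draw time happened to differ systematically between outcome groups, a spurious relation could appear, though nothing in the documents shows that it would. The Originality section of Project 2 hopes that the level will predict response and neuropathy in practice. A level without a time reference is a weak basis for that use, and times not noted at the visit are hard to recover later.

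**Working it through.** Project 2 gives no power or sample-size calculation, so there is no figure of the plan's to reproduce. The check sizes the timing effect.

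**Inputs from the documents:** 40 patients; daily dosing; five scheduled on-treatment levels (30 days and 3, 6, 9 and 12 months); no time-since-dose rule.

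**Inputs assumed, because the documents give none:** thalidomide half-life 4, 6, 8 or 12 h; draw times spread evenly over a 12-hour window (for example 2–14 h after dose); between-patient CV of exposure 30%, 40% or 70%; log-linear decline over the window.

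**Step 1. Fold change across the window:** 2^(12/half-life) = 8, 4, 2.8 and 2 for half-lives of 4, 6, 8 and 12 h.

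**Step 2. SD of the log level due to draw time:** (ln 2 / half-life) × (12 / √12) = 0.60, 0.40, 0.30 and 0.20. The variances are 0.360, 0.160, 0.090 and 0.040.

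**Step 3. Between-patient log variance:** ln(1 + CV²) = 0.086 at 30%, 0.148 at 40% and 0.399 at 70%.

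**Step 4. Reliability of one level** = between-patient variance / (between-patient variance + timing variance). For example, 4 h and 40%: 0.148 / (0.148 + 0.360) = 0.29.

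| CV | 4 h | 6 h | 8 h | 12 h |
|---|---|---|---|---|
| 30% | 0.19 | 0.35 | 0.49 | 0.68 |
| 40% | 0.29 | 0.48 | 0.62 | 0.79 |
| 70% | 0.53 | 0.71 | 0.82 | 0.91 |

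Timing accounts for more than half the variance where reliability is below 0.5, which is 5 of these 12 cells.

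**Step 5. Narrower window.** At 40% CV the range is 0.62–0.94 over 6 hours and 0.79–0.97 over 4 hours.

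**Step 6. Averaging.** If all five on-treatment levels were averaged and timing errors were independent between visits, the timing variance would be divided by 5. At 40% CV and a 12-hour window, reliability would then be 0.67–0.95.

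**Step 7. A second model.** A one-compartment steady-state simulation with first-order absorption (rate 0.5/h, assumed) and CV of 30–70% gives the share of log-level variance due to timing:

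| Draw window after dose | 6-h half-life | 12-h half-life |
|---|---|---|
| 1–24 h | 52–83% | 20–54% |
| 10–14 h | 4–16% | 1–5% |

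With half-lives of 3–48 h and draws at 1–24 h, the share runs from about 1% to 95%.

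**Step 8. Cost at n = 40.** Observed correlation = true correlation × √reliability. By Fisher's z at two-sided 5% (assumed), power = Φ(atanh(r)·√37 − 1.96). A true correlation of 0.4 gives 73% power. With attenuation factor 0.8 (reliability 0.64) r is 0.32 and power 52%; with factor 0.6 (reliability 0.36) r is 0.24 and power 32%.

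**The case against.** The strongest reply is that the size of the problem rests on three inputs the documents do not supply, and moderate choices make it modest. At 70% CV timing is never the larger part, and with draws inside four hours reliability at 40% CV is at least 0.79. This stands, and it limits the claim. A reader might infer that the level mainly reflects when the patient was bled; the documents do not support that, because it needs a short half-life together with widely scattered draws.

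A reader might also infer that the times will not be collected and that the data are beyond repair. The plan is silent, which is not the same. The AUC work needs sampling times at least in its ten patients, so the gap does not cover all of Project 2.

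Repeated sampling helps in principle, and the Justification speaks of longitudinal evaluation. But no averaging is specified, and a patient's visit hour may be much the same each time, so the errors may not be independent. Under the Safety section, patients without clinical response within 2 months leave the study; their only scheduled on-treatment level is day 30. Averaging is therefore least available in the non-responder group.

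Nor would a null result be meaningless. This is a declared convenience sample with no power claim, the result would be imprecise in any case, and the cytokines are separate primary exposures that this argument does not address.

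The Introduction's statement about independence from time and dose does not answer the point: it concerns the relation between saliva and plasma, not the level itself.

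**Conclusion.** The gap is real for the main cohort of 40: calendar visits only, no stated recording of last-dose and draw times, and no adjustment, for a variable named in the primary objective. The level is confounded by time since dose and may be dominated by it. How far cannot be settled from the documents. Under the assumed half-lives of 4–12 h and 12-hour window, between 9% and 81% of the log-level variance (1 minus reliabilities of 0.91 and 0.19) would come from draw time, less with tighter windows or averaged visits. The consequence is a noisier exposure measure and lower power. The change is worth making because it is cheap and has to be in place before the visits occur.

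A related matter remains: the dose at the draw can differ fourfold (100 to 25 mg/day) and depends on response, so the raw level also carries information about the outcome.

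**What to change.** 1. At every on-treatment visit, record the clock time of the last thalidomide dose and of the blood and saliva draws.
2. Schedule the draws within one common window after each patient's usual dose, by choosing the visit hour and leaving the dosing unchanged.
3. Pre-specify which level is analysed (for example day 30, the one scheduled on-treatment level that patients stopped for non-response also have), or how the levels are combined.
4. Include time since dose and current dose as covariates in the level–response and level–neuropathy analyses. Because dose reduction follows response, adjusting for dose will not fully separate exposure from outcome at later visits; say so when interpreting them.
5. A model-predicted AUC can serve as a sensitivity analysis, noting that the planned model rests on ten patients at 50 and 100 mg/day while the cohort may also take 25 mg/day.

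The cost is two extra recorded times per visit, some constraint on visit hours, and two covariates in a sample of 40.

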Histological sections submitted to immunohistochemistry techniques to demonstrate cellular and cytokine elements will be digitized by the Panoramic Scan (3D Histech, Hungary) scanner to obtain virtual histological slides. The reading of the material and capture of the images to be analyzed will be carried out with the program Panoramic Viewer version 1.15.2.21080 (3D Histech, Budapest, Hungary). The quantification of immune tagged cellular elements will be performed with the aid of image analysis program Image Pro Plus version 4.5.0.29 (MediaCybernetics Inc. , Rockville, MD, USA).

The quantification of fine nerve fibers will be performed by counting intraepidermal nerve fibers per millimeter of dermal epidermal junction and the relationship between area of marked subepidermal nerve fibers and total area of papillary dermis examined (Rodrigues Júnior, 2011).

Safety

Patients who fit the safety recommendations of the Ministry of Health will be included.

Clinical (with special attention to symptoms of peripheral polyneuropathy) and laboratory of adverse effects (including leukocyte count) will be performed at the entrance into the study and each medical consultation.

The ENMG will be performed to include in the study, at 6 months and at the end of the study.

If there is no clinical response within 2 months of the use of thalidomide, or in the clinical suspicion or enmg of peripheral neuropathy at any time, thalidomide will be suspended (out of the study) and follow-up of the patient will be continued in the outpatient clinics of the Rheumatology and Dermatology Services of HC-FMUSP.

WITHDRAWALS

See item Security.

ORIGINALITY WITH CARE IMPACT

There are no studies correlating tissue expression of cytokines with blood and salivary levels of thalidomide and its possible role as a predictor of response and adverse effects in patients in skin lesions of SLE. In addition, there are no studies on the value of skin biopsy in the diagnosis of thalidomide-induced neuropathy.

The expected impact with the availability of blood and salivary dosage of thalidomide in clinical practice is that this parameter may be a predictor of clinical response and neuropathy.

ADVANCES IN MECHANISM

The expected advance is a better understanding of the role of thalidomide in the expression of cytokines in the cutaneous lesion of SLE.

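### Project 2 takes nerve-fibre biopsies from the same patients at baseline and month 6, but plans no paired or baseline-adjusted analysis of fibre density, so change on treatment goes untested

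*Combined protocol and SAP*

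**What the plan says.** The Study Design section of Project 2 sets two biopsies per patient: "Skin biopsies of uninjured skin will be obtained from the thigh area, at baseline and at 6 months for the fine fiber neuropathy assessment". Under Histological analyses the measurement is quantitative. One measure comes from "counting intraepidermal nerve fibers per millimeter of dermal epidermal junction", the other is the ratio of subepidermal fibre area to papillary dermis area.

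The related secondary objective is to "Evaluate the presence of fine fiber neuropathy in skin biopsy specimens", with no cut-off given. Under Advances in Mechanism the aim is put more ambitiously: "we hope to determine whether the mechanism of thalidomide-induced neuropathy would target thin nerve fiber injury to histological skin analysis".

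The Statistical Plan has two sentences. The first covers group comparisons: "Patients with vs. without therapeutic response to thalidomide and vs. without signs of peripheral polyneuropathy will be compared for categorical variables by fisher's exact or". It goes on to name a second test for categorical data, and then deals with measured values such as fibre density: "quantitative variables, by t-Student or Mann-Whitney tests, when applicable". The second announces a multivariate analysis of influences on disease activity and polyneuropathy, without naming covariates or time points.

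Entry requires "NORMAL ENMG at study entry" and no history of peripheral neuropathy. There is no entry criterion on fibre density.

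**The concern.** A baseline biopsy is worth taking mainly so that the month-6 biopsy can be read against it. The plan collects that pair and then names no analysis that uses it as one. Every named test compares different patients with each other, and the multivariate analysis has polyneuropathy and disease activity as its outcomes, not fibre density.

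Two things are at stake. First, if thalidomide thins the fibres of most patients, a comparison of patients with and without neuropathy signs can miss it, because both groups move together. Second, a patient may enter with few fibres despite a normal ENMG. The protocol itself presents skin biopsy as a route to a more accurate and earlier diagnosis than ENMG, so it cannot assume that a normal ENMG rules out thin-fibre loss. Unless the baseline value enters the analysis, such loss may not be told apart from loss during treatment.

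**Working it through.** Project 2 has no sample-size calculation to reproduce: the 40 patients are a convenience sample. The figures below are illustrations.

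**Inputs from the documents**
- 40 patients, single arm (Number of Individuals).
- Neuropathy in 27% of patients in the retrospective study cited in the Justification: 0.27 × 40 = 10.8, about 11 v 29.
- Response in 81% in the same study: 0.81 × 40 = 32.4, so about 8 non-responders.
- Patients without a response within 2 months, or with suspected neuropathy at any time, leave the study (Safety).

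**Assumptions not in the documents for Project 2**
- Two-sided 5% level and 80% power.
- Correlation ρ between the two biopsies of 0.3 to 0.8 (0.7 in the simulations).
- Effects in units of the between-patient SD.

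**Step 1: what a group comparison can see.** Let the two groups have baseline means μ₁ and μ₂, and let everyone fall by δ. The month-6 difference is (μ₁ − δ) − (μ₂ − δ) = μ₁ − μ₂, so δ cancels. If change scores are compared instead, the difference is (−δ) − (−δ) = 0. Either way, a fall common to all patients is invisible.

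**Step 2: simulation** (4,000 runs, 11 v 29, ρ = 0.7). The table gives the share of runs with p < 0.05.

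| Scenario | Groups at month 6 | Groups on change | Paired, all 40 |
|---|---|---|---|
| All fall by 0.5 SD | 4.7% | 5.0% | 97% |
| Neuropathy group starts 0.5 SD lower, no change | 28% | 4.9% | 5.1% |
| Neuropathy group starts 1 SD lower, no change | 78% | 4.6% | 4.6% |

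The first row is Step 1 in numbers: the group tests reject at about the 5% error rate. The other rows show that a test on month-6 values alone would often be positive when nobody lost any fibres.

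**Step 3: what a paired test could detect.** The SD of the change is SD × √(2(1 − ρ)), a factor of 1.183 at ρ = 0.3, 1.000 at 0.5 and 0.632 at 0.8. By the noncentral t distribution, the detectable mean change in units of the SD of change is 0.454 with 40 pairs, 0.511 with 32 and 0.643 with 21. Here 32 = 40 − 8 non-responders, and 21 = 32 − 11 neuropathy exits as a worst case. Multiplying by the factor gives the detectable change in between-patient SDs:

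| Pairs | ρ = 0.3 | ρ = 0.5 | ρ = 0.8 |
|---|---|---|---|
| 40 | 0.54 | 0.45 | 0.29 |
| 32 | 0.60 | 0.51 | 0.32 |
| 21 | 0.76 | 0.64 | 0.41 |

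For a fall of 0.5 SD, power at ρ = 0.3 and 0.5 is 0.74 and 0.87 with 40 pairs, 0.64 and 0.78 with 32, and 0.45 and 0.59 with 21.

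**The case against.** The plan does not say which fibre value enters the group tests. A t or Mann-Whitney test on change scores would fit its wording, and the multivariate analysis could include baseline density. This stands against one tempting inference, that fibre loss present at entry will be counted as drug injury. No section says that, the baseline biopsy records such loss, and known neuropathy is screened out at entry. The documents support only that old and new loss may not be separated. The objection does not rescue the plan on change itself: as Step 1 shows, comparing change scores between groups still cannot show a fall shared by all.

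The mechanistic aim concerns thalidomide-induced neuropathy, so comparing patients with and without it is a relevant contrast, and the listed objective of presence can be met descriptively. That is fair. The group comparison should stay, adjusted for baseline, as the second analysis.

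A before-after change in a single arm does not isolate the drug either. Lupus continues, hydroxychloroquine is given alongside unless contraindicated, and prednisone may be tapered. Patients most likely to lose fibres may leave before month 6, so the completed pairs could understate loss. Both points stand and limit what the fix can deliver.

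Finally, this is a secondary objective in a convenience sample. That limits its weight, but the data are already being collected.

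**Conclusion.** The concern holds in a limited form. The biopsies are paired and quantitative, and no paired or baseline-adjusted analysis of them is specified. Change on treatment therefore has no test. That conclusion rests on the text alone. How far pre-existing loss would distort a group comparison depends on which values are analysed, which the plan leaves open.

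The power figures rest on assumed correlations and on the attrition assumed in the working. They show that a paired analysis is feasible for moderate changes if most pairs are complete, and weaker if many patients leave.

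A reader might also set the 11 v 29 comparison, which detects 1.02 SD at 80% power, against the paired figures and conclude that pairing is several times more sensitive. The documents do not support such a ratio. One figure is a difference between groups and the other a mean change within patients. The count of 11 is also doubtful at month 6, since the Justification places the onset of neuropathy at around 14 months of treatment.

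**What to change.** Amend the Project 2 Statistical Plan as follows:

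- Make within-patient change from baseline to month 6 the main biopsy analysis, for both intraepidermal fibre density and the subepidermal fibre-area ratio. Use a paired t or Wilcoxon signed-rank test with a 95% confidence interval.
- Compare patients with and without neuropathy on month-6 density adjusted for baseline density.
- Count only loss relative to the patient's own baseline as treatment-emergent. If presence of fine-fibre neuropathy is to be reported, state how it is defined.
- Report how many month-6 biopsies are missing and why, separating exits for suspected neuropathy from exits for non-response.
- State that, without an untreated control, the change cannot be attributed to thalidomide alone.
- Give any power figures only as illustrations, with the assumed correlation and number of pairs.

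The cost is a few sentences of text and no additional biopsy. The wording will not by itself solve selective loss of month-6 biopsies or the lack of a control, so the conclusions should be framed accordingly.

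### The thalidomide PK-PD model is to be fitted to SLEDAI-2K, which is not among the outcomes the plan lists for that model (change in CLASI, plasma TNF-alpha and IFN-1)

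*Combined protocol and SAP*

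**What the plan says.** Project 2 lists a PK-PD model of thalidomide dose reduction in SLE as a secondary objective. Its Study Design assigns the model to two groups of 5 patients on different doses and gives the timing as "Outcomes: evaluations on days 0 and 30". Two outcomes follow. Under (a): "Change in CLASI score assessing the activity/severity criteria from 0 to 70 will be performed", with a fall meaning improvement of the lupus skin injury. Under (b), headed "b) Cytokine dosage", are plasma TNF-alpha and IFN-1. SLEDAI-2K is not on this list.

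The Pharmacokinetic analysis paragraph under Relevant Methods then states what the model will use: "total and free plasma concentrations of thalidomide and, as a pharmacodynamic parameter, we will use the clinical/laboratory indices obtained by the evaluation of SLEDAI-2K". It mentions neither CLASI nor the cytokines.

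Elsewhere in the Study Design the two scores have separate jobs. SLEDAI-2K measures "the global activity of the disease through the SLEDAI-2K", and CLASI measures skin activity and severity.

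**The concern.** A concentration-effect model is defined by its effect variable. Here the outcome list and the modelling paragraph give different ones, and nothing in Project 2 reconciles them. An analyst who follows the modelling paragraph would fit a global lupus score in a project about cutaneous lupus and leave the listed outcomes unmodelled. An analyst who follows the outcome list would depart from the stated method.

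Two things are at stake. First, the dose-reduction model may not describe the response for which its patients were entered. Second, with two specifications on file, the effect variable could be chosen after the data are seen, and a reader of the report could not tell which model had been planned.

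**Working it through.** No arithmetic settles this. Project 2 is a convenience sample with no power calculation, so there is no planned figure to reproduce. The check sets the two PK-PD components of the protocol side by side.

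| | Subproject 1B (hydroxychloroquine) | Project 2 (thalidomide) |
|---|---|---|
| Patients | two groups of 5 | two groups of 5 |
| Assessments | days 0 and 120 | days 0 and 30 |
| Listed outcome (a) | change in SLEDAI-2K | change in CLASI |
| Listed outcome (b) | plasma TNF-alpha, IFN-1 | plasma TNF-alpha, IFN-1 |
| Pharmacodynamic parameter in Relevant Methods | SLEDAI-2K | SLEDAI-2K |
| Agreement with (a) | yes | no |
| Agreement with (b) | no | no |

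1. In subproject 1B the modelling sentence agrees with that model's clinical outcome. In Project 2 nearly the same sentence appears with the drug name changed, but the clinical outcome is now CLASI. Text carried over from 1B is a likely explanation. The documents do not prove it, and the mismatch stands whatever its cause.

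2. What Project 2 is aimed at. Its title is about treating cutaneous lupus, entry requires active skin lesions, and the justification presents thalidomide as inducing remission of skin activity. The listed clinical PK-PD outcome is improvement of the skin.

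3. What the global score covers. Subproject 1B describes SLEDAI-2K as running from 0 to 105 over 9 organs and 24 items. Project 2 excludes patients with concomitant "Renal and/or central nervous system and/or hematological activity", the last of these specified as haemolytic anaemia or platelets below 50,000. So 3 of the 9 organs are restricted at entry, one of them only in part, and 9 − 3 = 6 are not mentioned. The range the global score can show at entry is probably narrower, but most of its organs remain.

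4. Amount of data. There are 5 + 5 = 10 patients with two assessments each, hence 10 × 2 = 20 effect values, or 10 changes from day 0 to day 30.

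5. Availability. The Study Design schedules both SLEDAI-2K and CLASI at baseline and 1 month, and the cytokines at time zero and 30 days. Any of the candidate effect variables can be modelled from data already planned.

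**The case against.** The strongest reply is that the model can be fitted as written. SLEDAI-2K is a scheduled Project 2 assessment at the right times, and the secondary objective speaks of patients with SLE without restricting the model to skin. CLASI, as the protocol describes it, also combines erythema with scarring, hypertrophy and atrophy, so it is not self-evidently the ideal 30-day effect measure. And because both scores are collected, no information is lost if the choice is settled before modelling.

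Most of that stands. It shows that the choice of CLASI rests on inference from the plan's own outcome list and its cutaneous focus. It does not remove the conflict: SLEDAI-2K is still absent from the outcomes listed for this model, and the listed outcomes are still absent from the modelling paragraph.

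A reader might go further and infer that most of the SLEDAI-2K organ systems cannot respond in these patients, or that a model fitted to it would carry almost no effect signal. The documents support neither. The exclusions touch three of nine organs, the haematological one only in part, and every patient enters with active skin disease. The protocol gives no item weights and no expected change for either score, so sensitivity cannot be derived from it. Setting a 0–105 range beside a 0–70 range does not measure sensitivity either. Nor would a change of score cure the small sample: 10 patients with two assessments each is a limit under any effect variable.

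**Conclusion.** The point holds as an unresolved contradiction. Followed literally, the thalidomide PK-PD model would not describe any of the outcomes listed for it, and it would use a global score where the plan's stated interest is the skin. That the global score is less direct here follows from the plan's own descriptions of the two indices, the entry criteria and the exclusions. How much less sensitive it is cannot be quantified from the documents.

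The reach is small: one secondary objective, 10 patients, no hypothesis test or power claim attached. The primary objective and the 40-patient comparisons of responders with non-responders, and of patients with and without polyneuropathy, are unaffected. The preference for CLASI assumes that the outcome list states the sponsor's intention. If the sponsor does intend SLEDAI-2K, the outcome list is the text that needs amending, with a reason given.

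**What to change.** Amend the modelling sentence in Project 2, Relevant Methods, Pharmacokinetic analysis, so that it:

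- names change in CLASI from day 0 to day 30 as the main pharmacodynamic variable;
- states whether plasma TNF-alpha and IFN-1 are also modelled and, if so, in what role;
- keeps SLEDAI-2K as a secondary effect measure.

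Make the change before any PK-PD modelling starts, so that the effect variable is fixed in advance. The cost is a sentence or two of text. It needs no new visit, sample or patient, and no dose or clinical rule changes. The write-up should still present the model as exploratory, because the number of patients stays at 10.
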